## **10.2 Baseline (Within 1 Week ( $\leq$ 7 Days) Before the First Vicinium Treatment)**

The following assessments and procedures must be conducted within the week before first dose of study drug administration:

- Laboratory assessments ([Section 16.2](#))
- Complete physical examination, including height and weight ([Section 16.3](#))
- Blood sample for determination of plasma anti-Vicinium antibodies
- Urine or serum pregnancy test (females of childbearing potential only)
- Current medication history including prescription medications, over-the-counter medications, vitamins, supplements, herbal and homeopathic treatments

## 10.3 Induction Phase

During the 12-week Induction Phase, subject will treated twice weekly for 6 weeks followed by once weekly treatment for 6 weeks

Assessments during the Induction Phase are as follows:

### 10.3.1 Week 1 (Twice Weekly Dosing)

Assessments during week 1 are as follows:

Assessment	Week 1 First Dose		Week 1 Second Dose	
	Pre-Dose	Post-Dose	Pre-Dose	Post-Dose
Urine Cytology	✓			
Chemistry	✓ 			
Hematology (CBC and differential)	✓ 			
Urinalysis	✓ 			
Plasma Vicinium Level	✓	✓ 		
Physical Examination	✓ 			
Vital Signs	✓	✓	✓	✓
Adverse Event Assessment	✓	✓	✓	✓
Concomitant Medications	✓	✓ 	✓	✓ 

1 Chemistry, hematology, urinalysis ([Section 16.2](#)): Required only if not obtained in baseline period (within 7 days for first dose of Vicinium)

2 Obtain at the end of the dwell time as soon as possible after the subject voids (or bladder is drained via catheter)

3 Required only if not obtained in the baseline period ([Section 16.3](#))

4 Required only if additional medications (not including Vicinium) were administered during or after the start of the instillation

### 10.3.2 Weeks 2-5 (Twice Weekly Dosing)

Assessments during weeks 2-5 are as follows:

Assessment	Week 2 - 5 First Dose Each Week		Week 2 – 5 Second Dose Each Week	
	Pre-Dose	Post-Dose	Pre-Dose	Post-Dose
Hematology (CBC and differential)			✓ 	
Chemistry			✓ 	
Vital Signs	✓	✓	✓	✓
Adverse Event Assessment	✓	✓	✓	✓
Concomitant Medications	✓	✓ 	✓	✓ 
Targeted Physical Examination and Weight	Week 4			
Pregnancy Test	Week 4			

1 Chemistry laboratory tests should be drawn up to one day before the 2nd dose of the week and results must be reviewed prior to administration of the 2nd dose of the week. With Sponsor approval, the chemistry laboratory tests may be drawn up to one day before the 1st dose of the week and results must be checked prior to administration of the 1st dose of the week. For extreme logistical/laboratory limitations at the site or undue burden on the subject, the sponsor may approve that labs can be drawn up to 2 days before dosing. Hematology tests should be drawn at the same time as chemistry tests for subject convenience ([Section 16.2](#)).

2 Required only if additional medications (not including Vicinium) were administered during or after the start of the instillation

3 A pregnancy test (urine or serum) is required in week 4 for all WOCBP

### 10.3.3 Week 6 (Twice Weekly Dosing)

Assessments during week 6 are as follows:

Assessment	Week 6 First Dose		Week 6 Second Dose	
	Pre-Dose	Post-Dose	Pre-Dose	Post-Dose
Chemistry			✓ 	
Hematology			✓ 	
Plasma Vicinium Level				✓ 
Urinalysis			✓ 	
Vital Signs	✓	✓	✓	✓
Adverse Event Assessment	✓	✓	✓	✓
Concomitant Medications	✓	✓ 	✓	✓ 

1 Chemistry laboratory tests should be drawn up to one day before the 2nd dose of the week and results must be reviewed prior to administration of the 2nd dose of the week. With Sponsor approval, the chemistry laboratory tests may be drawn up to one day before the 1st dose of the week and results must be checked prior to administration of the 1st dose of the week. For extreme logistical/laboratory limitations at the site or undue burden on the subject, the sponsor may approve that labs can be drawn up to 2 days before dosing. Hematology tests should be drawn at the same time as chemistry tests for subject convenience ([Section 16.2](#)).

2 Obtain at the end of the dwell time as soon as possible after the subject voids (or drug is drained via catheter)

3 Required only if additional medications (not including Vicinium) were administered during or after the start of the instillation

#### 10.3.4 Weeks 7-11 (Once Weekly Dosing)

Assessments during weeks 7-11 are as follows:

Assessment	Week 7-11	
	Pre-Dose	Post-Dose
Hematology (CBC and differential)	✓ 	
Chemistry	✓ 	
Vital Signs	✓	✓
Adverse Event Assessment	✓	✓
Concomitant Medications	✓	✓ 
Targeted Physical Examination and Weight	Week 8	
Pregnancy Test	Week 8	

 Laboratory tests will be drawn at least 3 days after the prior week's dose and within 4 days of the current week's planned Vicinium dose. The results must be reviewed prior to administration of the dose.

 Required only if additional medications (not including Vicinium) were administered during or after the start of the instillation

 A pregnancy test (urine or serum) is required in week 8 for all WOCBP

### 10.3.5 Week 12 (Once Weekly Dosing)

Assessments during week 12 are as follows:

Assessment	Week 12	
	Pre-Dose	Post-Dose
Urine Cytology	✓	
Urinalysis	✓ 	
Hematology (CBC and differential)	✓ 	
Chemistry	✓ 	
Plasma Vicinium Level (Pharmacokinetics)		✓ 
Vital Signs	✓	✓
Adverse Event Assessment	✓	✓
Concomitant Medications	✓	✓ 
Targeted Physical Examination and Weight		✓
Triple ECGs		✓
Anti-Vicinium Antibodies		✓
Pregnancy Test		✓

1 Chemistry and hematology laboratory tests drawn at least 3 days after the Week 11 dose and within 4 days prior to the Week 12 dose and results must be reviewed prior to administration of the dose ([Section 16.2](#)).

2 Obtain at the end of the dwell time as soon as possible (i.e., within 30 minutes) after the subject voids (or the bladder is drained via catheter)

3 Required only if additional medications (not including Vicinium) were administered during or after the start of the instillation

4 A pregnancy test (urine or serum) is required in week 12 for all WOCBP

### 10.4 Post-Induction Phase Evaluation

Subjects will be evaluated for disease status at the end of the Induction Phase. Urine cytology is obtained in week 12 as described above. Starting in week 13 (or as soon as possible after week 12) subjects will undergo cystoscopy and directed biopsies/TURBT of all lesions suspicious for disease. Subjects are eligible to receive Maintenance Phase treatment if they do not have a protocol defined treatment failure (see [Section 14.2](#)) or other criteria for study drug discontinuation (see [Section 14.3](#)) and are tolerating treatment.

See [Section 14.4](#) for criteria to continue treatment.

### 10.5 Maintenance Phase

Disease evaluation will be performed every 13 weeks regardless of dose interruptions or delays (see [Section 14.4](#)). Cystoscopy and urine collection for cytology during the Maintenance Phase should be done at Week 26, Week 39, Week 52, Week 65, Week 78, Week 91, and Week 104, even if there are

missed doses or dosing delays. Every effort should be made to stay on this evaluation schedule, however, a window of one week before and up to 2 weeks after these time points is permitted (e.g., the Week 26 cystoscopy and urine for cytology may be performed from Week 25 to Week 28, but as close to week 26 as possible). The complete evaluation to determine disease status (e.g., repeat cytology, cystoscopy and biopsies if required) should be completed as soon as possible following the every 13-week timepoint. Vicinium dosing may continue during these disease evaluations in the Maintenance phase per investigator discretion. Vicinium treatment should not be given within 2 weeks of any biopsy/TURBT.

Other assessments during the Maintenance Phase are as follows:

#### **10.5.1 Treatment Days**

Assessment	Treatment Days	
	Pre-Dose	Post-Dose
Vital Signs	✓	✓
Adverse Event Assessment	✓	✓
Concomitant Medications	✓	✓ 

 Required only if additional medications (not including Vicinium) were administered during or after the start of the instillation

#### **10.5.2 Every 2 weeks**

- Chemistry (see [Section 16.2](#)). Sample should be drawn at least 7 days after the prior dose and within 5 days prior to day of next dosing and results must be reviewed prior to dosing.

#### **10.5.3 Every 4 weeks**

- Hematology (see [Section 16.2](#))
- Urinalysis (see [Section 16.2](#))
- Targeted physical examination ([Section 16.3](#))
- Weight
- Pregnancy test

#### **10.5.4 Between Week 23 – Week 27**

- Plasma sample for anti-Vicinium antibodies

### **10.6 Post-Treatment Evaluation**

Subjects will return to the clinic site for a Post-Treatment evaluation 30 – 37 days after their last dose of study treatment.

The following assessments will be performed at that time

- Targeted physical examination (including weight) ([Section 16.3](#))

- Triplicate ECG obtained within 30 minutes of each other at least 3 minutes apart
- Vital signs
- Concomitant medications
- Adverse events, including SAEs
- Collection of clinical laboratory samples: blood samples for hematology and chemistry, urine samples for urinalysis
- Anti-Vicinium antibodies
- Blood or urine pregnancy test (WOCBP)
- The following are to be done if the subject has not discontinued treatment due to documented disease recurrence, progression and if they have not been performed within the past 8 weeks
  - Cystoscopy
  - Biopsy (directed). EpCAM determination by immunohistochemistry will be obtained on all positive biopsies.
  - Urine cytology

As described in **Section 15**, additional follow-up will occur for subjects with ongoing clinically significant AEs (e.g., those leading to study drug discontinuation) or SAEs assessed as related to study drug.

Subjects without a treatment failure (see **Section 14.2**) will continue to undergo evaluations for disease status (urine cytology, cystoscopy, directed biopsies) every 13 weeks until the sooner of a treatment failure or the determination of the 18-month event free survival analysis. Survival data also will be collected on subjects every 13 weeks. Once all subjects are no longer receiving study treatment and the 18-month event-free survival for the study is determined, the study will close and subjects will then be followed by their physician according to standard of care.

**Table 3: Visit Schedule and Assessments [Screening & Induction]**

Assessment	Screening and Baseline Weeks		Induction Phase Weeks 1- 12					Post-Induction Phase	
	Week	-8 through -1	-1	1	2-5	6	7-11	12	
Informed consent	X								As soon as possible after Week 12
Inclusion/Exclusion criteria	X								
Cystoscopy	X 								X 
Bladder biopsy/TURBT	X 								X 
EpCAM determination, Biomarker evaluations 	X 								X 
Urine Cytology				X 				X 	
Demographics	X								
Medical and medication history (including previous anti-tumor therapy and surgical procedures)	X	X 							
Physical examination		X	X 	X 		X 	X 		
Weight and height		X 		X 		X 	X 		
Radiological imaging	X 								
Triple ECG	X 							X 	
Vital signs	X		X 	X 	X 	X 	X 		
Hematology		X	X 	X 	X 	X 	X 		
Chemistry		X	X 	X 	X 	X 	X 		
Urinalysis		X	X 		X 			X 	
Anti-Vicinium antibody test		X						X	
Plasma Vicinium Levels (PK) 			X		X			X	
Serum or urine pregnancy test		X 		X 		X 	X 		
Concomitant medication			X 	X 	X 	X 	X 	X 	X
Adverse events (AEs / SAEs)			X 	X 	X 	X 	X 	X 	X
Drug administration (BIW) 			X	X	X				
Drug administration (once/week)						X	X		

 Must have documented non-muscle invasive urothelial bladder cancer that is histologically confirmed by the independent central pathology reviewer prior to the first dose of study drug. All papillary disease must be completely resected. In subjects with T1 disease, a second (i.e., restaging) TURBT must be performed approximately 2 - 6 weeks after the first. A biopsy may be more than 8 weeks prior to the first dose of study drug as long as the last biopsy that confirms eligibility is within 8 weeks.

 White-light cystoscopy. Any subject who undergoes fluorescence cystoscopy for bladder biopsy/TURBT during the screening period must continue having this modality for all subsequent biopsies (however, white-light cystoscopy will suffice for all assessments if a biopsy is not required ([Section 14](#))).

 Directed biopsies of all areas suspicious for disease. Random biopsies are required if cystoscopy is negative and urine cytology is positive or there are two suspicious cytology results ([Section 14](#))

 CT urogram or MRI urogram. If intravenous contrast is contraindicated, retrograde ureteropyelography, or CT or MRI without intravenous contrast may be performed. Required during Screening for all subjects with T1 disease. Required for all other subjects if not previously performed within 13 weeks before the start of dosing.

 Single tracing only at Screening unless QTc is prolonged ([Section 16.4](#)); thereafter, triplicate ECGs are to be performed.

 Update medication history.

 Performed every 4 weeks (i.e., week 4, week 8, week 12, etc.) while on treatment in females of childbearing potential only.

 Cytology sample pre-dose on Day 1. Note: Chemistry, hematology (CBC and differential), urinalysis and physical examination need to be performed pre-dose Day 1 only if not performed in the Baseline Period ( $\leq 7$  days before the first dose of study medication).

 Evaluation performed pre-dose and post-dose prior to leaving the clinic.

 Evaluation performed pre-dose. Concomitant medications required post-dose only if additional medications (not including Vicinium) were administered during or after the start of the instillation.

 Weeks 2-5: Chemistry and hematology (CBC and differential) performed once weekly ([Section 10.3.2](#)). Week 4: Targeted physical examination. Week 6: Urinalysis performed pre-dose at the second dose of the week; Hematology (CBC and differential) and chemistry ([Section 10.3.3](#)). Weeks 7-11: Chemistry and hematology (CBC and differential) performed once weekly ([Section 10.3.4](#)). Week 8: Targeted physical examination. Week 12: Urinalysis performed pre-dose. Hematology (CBC and differential), chemistry([Section 10.3.5](#)). Targeted physical examination, and triplicate ECG performed post-dose prior to leaving the clinic.

 Height and weight at Baseline. Weight performed Week 4, Week 8 and Week 12.

 Twice weekly (BIW) dosing with each dose separated by at least 48 hours (and no more than 2 doses within any calendar week (Sunday through Saturday)). As an example, while a Monday/Thursday or Tuesday/Friday would be optimal, a Monday/Wednesday or Tuesday/Thursday, or Wednesday/Friday dosing schedule could be used.

 Levels are to be taken pre-dose of first instillation. Additional sampling is at the end of the dwell time as soon as possible (within 30 minutes) after the subject voids (or bladder is drained via catheter) following the first instillation and after the second of the twice-weekly instillations during Weeks 6 and 12.

 For all bladder biopsy/TURBT samples positive for urothelial carcinoma ([Section 16.7](#)).

**Table 4: Visit Schedule and Assessments (Maintenance Phase)**

Assessment	Maintenance Phase					Post-Treatment (30 – 37 days after last dose)
	Treatment Days	Every 2 Weeks	Every 4 Weeks	Every 13 Weeks	Between Weeks 23 and 27	
Cytology				X 		X 
Cystoscopy				X 		X 
Biopsy/TURBT				X 		X 
Physical examination			X 			X 
Triplett ECG						X
Vital signs	X 					X
Weight			X			X
Anti-Vicinium antibody test					X	X
Chemistry		X 				X
Hematology and urinalysis			X 			X
Urine or serum pregnancy test			X 			X
Concomitant medication	X 					X 
Adverse events (AEs / SAEs)	X 					X
Drug administration (once every other week)	X					
Contact to assess for progression and survival				X 		

 Window of 1 week before to 2 weeks after to start evaluation

 White-light cystoscopy. Any subject who underwent fluorescence cystoscopy for bladder biopsy/TURBT during the screening period must continue having this modality for all subsequent biopsies (however, white-light cystoscopy will suffice for all assessments if a biopsy is not required ([Section 14](#))).

 Directed biopsies of all areas suspicious for disease. Random biopsies are required if cystoscopy is negative and urine cytology is positive or there are two suspicious cytology results ([Section 14](#))

 Evaluation performed pre-dose and post-dose prior to leaving the clinic. Concomitant medications required post-dose only if additional medications (not including Vicinium) were administered during or after the start of the instillation

 Performed every 4 weeks during study participation in females of childbearing potential only.

 Evaluations performed if the subject has not discontinued treatment due to documented disease recurrence, progression and if they have not been performed within the past 8 weeks.

 Targeted physical examination.

 Additional follow-up will occur for subjects with ongoing clinically significant AEs (e.g., those leading to study drug discontinuation) or SAEs assessed as related to study drug.

 Urinalysis performed pre-dose if on a treatment day.

 Weeks 26, 39, 52, 65, 78, 91, 104

 Starting after subject discontinues study drug. Progression will be assessed if the subject did not have disease progression as the reason for discontinuation of study drug and has not had a cystectomy.

 [Section 10.5.2](#).

 EpCAM and biomarker evaluation on all bladder biopsy/TURBT samples positive for urothelial carcinoma ([Section 16.7](#)).

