The usual first treatment for NMIBC (Ta, T1, and CIS) is transurethral resection of the bladder tumors (TURBT), followed by intravesical immunotherapy, most commonly with bacillus Calmette-Guérin (BCG). ([Babjuk 2013, American Urological Association 2014](#)) In patients with T1 tumors, a second TURBT is recommended. ([Babjuk 2013, American Urological Association 2014](#)) Induction therapy with BCG is usually dosed as 6 once-weekly instillations. ([Babjuk 2013, American Urological Association 2014](#)) In patients with high-grade Ta, T1, and CIS, maintenance therapy with BCG of at least 1 year is recommended, ([Babjuk 2013, Anastasiadis 2012](#)) although the optimal dose, dosing schedule, and duration of treatment are unknown. ([American Urological Association 2014](#)). Local and systemic side effects are common with intravesical BCG therapy, causing discontinuation of treatment in approximately 20% of patients. ([Sylvester 2011](#)) Approximately 75% of patients experience local side effects (including cystitis, irritative voiding symptoms, and hematuria), while 40% report systemic side effects, including general malaise and fever. ([Sylvester 2011](#)) Intravesical BCG failure occurs in up to 40% of patients. ([Sylvester 2011](#)) Because of the high risk for development of muscle invasive disease, cystectomy is recommended for CIS and high-grade Ta and T1 patients who experience disease recurrence following intravesical therapy. ([Babjuk, 2013, American Urological Association 2014](#)) For patients unable or unwilling to undergo cystectomy, treatment options are limited.

Vicinium™ (Vicinium) contains the active pharmaceutical ingredient VB4-845, which is a recombinant fusion protein produced in *Escherichia coli* (*E. coli*) that expresses a humanized single-chain antibody fragment (scFv) specific for the epithelial cell adhesion molecule (EpCAM) antigen linked to ETA(252-608). ETA(252-608), which is a truncated form of *Pseudomonas* exotoxin A (ETA) that lacks the cell binding domain, is a single polypeptide fusion protein produced by continuous translation of a single construct.

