### **11.3 Study Withdrawal Criteria**

Subjects are free to withdraw from treatment or from any further participation in the study (i.e., withdraw consent) at any time and without prejudice to further treatment. The Investigator should discuss with the subject if they want to withdraw from further treatment only (i.e., additional data will be collected) or from all further study participation at which time no data will be collected for the subject. The investigator must withdraw a subject from all further study participation if that subject withdraws consent. No additional evaluations will be done or data collected for subjects who withdraw consent. All subjects withdrawing from further study treatment should have Post-Treatment evaluation 30 – 37 days after the last dose of study treatment and receive follow up disease evaluation (every 3 months ([Section 10.6](#)) and until a protocol-defined event as well as be contacted for data secondary endpoint (PFS, OS). The reasons and details relevant to subject withdrawal must be recorded in the case report form (CRF). The Investigator must notify the Medical Monitor if a subject is withdrawn from the study.

Subjects must be withdrawn from study drug for any of the following reasons:

- Withdrawal of informed consent
- Pregnancy ([Section 12.5](#))
- Treatment failure ([Section 14.2](#))
- Documented extravesical (i.e., upper or lower tract) urothelial carcinoma
- Development of a second malignancy that requires systemic therapy
- Cystectomy
- Unacceptable toxicity
- Persistent non-compliance with the protocol requirements
- Treating physician / study Investigator concludes that it would be in the subject's best interest
- Intercurrent illness that, in the judgment of the Investigator, may affect assessments of clinical status to a significant degree, and that requires discontinuation of study drug.
- Sponsor terminates the study.

Subjects may be considered withdrawn if they fail to return for visits, or become lost to follow-up for any other reason. Every attempt should be made to re-establish contact for subjects who are lost to follow-up (i.e., those subjects whose status is unclear because they fail to appear for study visits without stating an intention to withdraw). The Investigator should undertake appropriate due diligence and document steps taken to contact the subject (e.g., dates of telephone calls, registered letters).

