Subjects' disease status will be evaluated based on cystoscopy (and biopsies if indicated) and urine cytology at the end the Induction Phase (week 13) and every 13 weeks during the Maintenance Phase (i.e., Week 26, Week 39, Week 52, Week 65, Week 78, Week 91, Week 104) regardless of dosing interruptions or delays. For subjects who discontinue treatment for reasons other than disease progression ([Section 14.2](#)), cystectomy or death, the every 13-week disease evaluation should continue for the determination of secondary endpoints e.g., event-free survival, progression-free survival. Every effort should be made to stay on this evaluation schedule, however, a window of one week before and up to 2 weeks after these time points is permitted (e.g., the Week 26 cystoscopy and urine for cytology may be performed from week 25 to week 28, but as close to Week 26 as possible). The complete evaluation to determine disease status may require a repeat cytology and repeat cystoscopy with biopsies (See [Table 7](#)) and should be completed as soon as possible following the every 13-week timepoint. On cystoscopy, any areas suspicious for disease must be biopsied. In situations where there are no suspicious lesions on cystoscopy but a positive or suspicious result on urine cytology, random bladder biopsies will be obtained from the locations of disease identified at Screening (i.e., by screening biopsies and the screening bladder mapping) and from other areas of the bladder so that all the following areas of the bladder have been biopsied: the dome, the posterior wall, the left and right lateral walls, the trigone and the bladder neck, and in males, the prostatic urethra. A second urine cytology will also be required at the time of evaluation if the result of the first urine cytology is suspicious for urothelial carcinoma. The use of other diagnostic evaluations (e.g. urine FISH) or the performance of additional urine cytology, cystoscopies, and/or biopsies not mandated by the protocol may be performed when clinically indicated per the investigator's clinical judgment or standard of care. Results of urine FISH will not be considered in the response evaluation but may be used by the investigator to guide additional (non-protocol mandated) evaluations.

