Progression-free survival (PFS) will be analyzed for subjects in Cohorts 1, 2 and 3 and is defined as the time from the date of first dose of study treatment to the date of disease progression (e.g., T2 or more advanced disease) or death on or prior to treatment discontinuation, whichever occurs first. Because disease assessments are not recorded after treatment discontinuation, a death after treatment discontinuation will not be counted as an event so as not to artificially inflate PFS. Subjects without disease progression or death will be censored at the last assessment.

Censoring rules for the analysis of PFS are presented in the table below.

Table: Censoring scheme for PFS in Cohorts 1, 2, and 3

Situation	Date of Event or Censoring	Outcome
Disease progression	Date of disease progression	Event
Death without disease progression and occurring prior to treatment discontinuation	Date of death	Event
Death without disease progression and occurring after treatment discontinuation	Date of last evaluable disease assessment on or prior to treatment discontinuation ^a	Censored ^a
No baseline disease assessment	Date of first dose	Censored
No on-study disease assessments and no death	Date of first dose	Censored
No disease progression and no death	Date of last evaluable disease assessment	Censored
New anti-cancer therapy received without treatment failure and reported prior to or on the same day as disease assessment	Date of last evaluable disease assessment on or prior to the date of initiation of subsequent therapy	Censored
Second non-NMIBC cancer reported prior to or on the same day as disease assessment	Date of last evaluable disease assessment on or prior to the date of diagnosis of non-NMIBC cancer	Censored
a This censoring rule acknowledges that disease assessments were not recorded after treatment discontinuation due to an AE.		

Overall Survival (OS)

Overall Survival (OS) is defined as the time from the date of first dose of study treatment to death due to any cause. Subjects who are alive will be censored at the date of last contact.

Fridericia Corrected QT (QTcF)

$$QTcF = \frac{QT}{\sqrt[3]{RR}}$$

Bazett Corrected QT (QTcB)

$$QTcB = \frac{QT}{\sqrt{RR}}$$

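### Progression assessment stops at cystectomy and PFS has no rule for the specimen, so T2 or worse disease found at surgery can go uncounted

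*Protocol*

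**What the plan says.** PFS in all subjects is a secondary endpoint in both documents. Protocol Section 17.5 lists it without defining it. SAP 3.3.7 measures it from first dose "to the date of disease progression (e.g., T2 or more advanced disease) or death on or prior to treatment discontinuation, whichever occurs first". The same section adds: "Because disease assessments are not recorded after treatment discontinuation, a death after treatment discontinuation will not be counted as an event". Its default is: "Subjects without disease progression or death will be censored at the last assessment". The PFS censoring table that follows has no row for cystectomy. For EFS, SAP 3.3.7 does give a rule: a subject without treatment failure who has a cystectomy is censored on that date.

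Four protocol passages govern what is collected after study drug stops:
- **Table 4, footnote 11** (and SAP 1.3, footnote 11): at the 13-weekly contact, progression is "assessed if the subject did not have disease progression as the reason for discontinuation of study drug and has not had a cystectomy".
- **Section 14**: for subjects who stop for reasons other than disease progression, "cystectomy or death, the every 13-week disease evaluation should continue for the determination of secondary endpoints".
- **Section 10.6**: disease evaluations continue for subjects without a treatment failure; survival data are collected every 13 weeks.
- **Section 11.3**: cystectomy and treatment failure both require withdrawal from study drug. Subjects withdrawn from treatment are followed for disease until a protocol-defined event, "as well as be contacted for data secondary endpoint (PFS, OS").

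SAP Section 1 states that the SAP prevails where the two documents differ.

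**The concern.** The subjects most likely to progress are those whose high-grade disease persists or returns. Section 7 of the protocol makes the link itself: "Because of the high risk for development of muscle invasive disease, cystectomy is recommended for CIS and high-grade Ta and T1 patients" who recur after intravesical therapy. A cystectomy specimen gives a pathological stage, and T2 in that specimen satisfies the SAP's description of progression. Yet surgery is the point at which the scheduled progression contact ends.

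If the finding is not recorded, or is recorded but not counted, the subject leaves the PFS analysis as censored. That censoring is informative, and the error runs one way: leaving out upstaged specimens can raise the PFS estimate but never lower it. Death does not act as a backstop, because a death after treatment discontinuation is not a PFS event either.

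**Working it through.** Neither document states a PFS rate, event count or power for PFS, so there is no planned figure to reproduce. The check is mainly one of text.

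**1. Follow one subject through the rules.** Take a hypothetical subject with high-grade disease at the Week 13 evaluation, cystectomy at Month 5, T2 in the specimen, and a later death.
- Week 13: treatment failure, so study drug stops (Section 11.3). Regular disease evaluations no longer apply (Sections 10.6 and 14). The footnote 11 contact is then the only scheduled source of progression data.
- Month 5: cystectomy. Footnote 11 ends progression assessment; Section 11.3 says PFS contact continues. The two cannot both be followed.
- Specimen: Section 10 sends diagnostic pathology, including bladder tissue, for central review; Section 14 names only cytology and biopsy samples. Neither names a cystectomy specimen or asks for its stage.
- PFS: if the T2 finding is in the data, the disease-progression row could make it an event. If it is not, the subject is censored at the last evaluable assessment, near Week 13.
- Death: it falls after discontinuation, so it is censored for PFS (it still counts for OS).

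**2. What a programmer could do with a cystectomy in PFS.** There are three defensible codings: count T2 in the specimen as progression; censor at the last assessment; or, in a subject without treatment failure, treat surgery as new anti-cancer therapy and censor at the last assessment before it. The SAP does not choose among them.

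**3. Size, on assumed rates.** N = 134 is from Protocol Section 17.8. The cumulative cystectomy rate c and the share u of specimens with T2 or worse are not in the documents; 10-30% is assumed for each.

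Subjects affected = 134 × c × u:
- c = u = 10%: 134 × 0.10 × 0.10 = 1.3
- c = u = 20%: 134 × 0.20 × 0.20 = 5.4
- c = u = 30%: 134 × 0.30 × 0.30 = 12.1

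These are upper figures for each pair of rates. A subject whose T2 disease was documented before surgery already has an event. With u = 0 nothing is lost.

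**4. Effect on a Kaplan-Meier estimate, illustration only.** Assume constant hazards and cystectomy independent of other progression. Let S0 be PFS at a fixed time with specimen findings not counted. Counting them gives S = S0 × (1 − c)^u. With S0 = 0.90 (assumed):
- 10%/10%: 0.90 × 0.90^0.10 = 0.891, overstated by 0.9 points
- 20%/20%: 0.90 × 0.80^0.20 = 0.861, overstated by 3.9 points
- 30%/30%: 0.90 × 0.70^0.30 = 0.809, overstated by 9.1 points

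With S0 = 0.80 or 0.95 the middle case gives 3.5 or 4.1 points, so the result depends far more on c and u than on S0.

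**The case against.** The strongest reply is that nothing here excludes the specimen. Footnote 11 governs a follow-up contact, not surgical pathology. The SAP's progression row restricts neither the tissue source nor the timing; the explicit discontinuation limit attaches to death. Section 11.3 calls for PFS contact after withdrawal, and Section 10 sends bladder tissue for central review. The SAP output list has a central pathology listing and a post-treatment follow-up listing. The absence of one labelled for cystectomy does not show that stage is uncollected, and the eCRF is not available to us. All of this stands. A reader might infer that T2 disease at cystectomy is never a PFS event; the documents do not say so.

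A second reply is that footnote 11 is not the main cause. If the SAP's statement on unrecorded assessments governs, progression after discontinuation is lost with or without surgery. That is partly right: the SAP text is the wider problem. Its table footnote is narrower, referring only to discontinuation for an AE, so the scope is itself unclear. But if the progression row is read as open-ended, footnote 11 matters, because it ends collection for cystectomy subjects while others are still contacted.

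Two further inferences are tempting and unsupported. No passage says that PFS is meant to show whether delaying cystectomy is safe, and neither document mentions nodal disease. PFS also carries no hypothesis or threshold, and the trial has no comparator arm.

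**Conclusion.** The point holds as a conflict and a missing rule. Footnote 11 and Section 14 end progression assessment at cystectomy; Section 11.3 does not. The SAP's PFS rules are silent on cystectomy although its EFS rules are not. Events that meet the plan's own definition can therefore be lost, in the direction that favours the drug. This is more than missing detail, because a stated stop rule causes the loss and deaths after discontinuation do not make it good.

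The size is unknown. About 1 to 12 of 134 subjects rests wholly on the assumed 10-30% rates, and the percentage-point figures add an assumed PFS level, constant hazards and independence. They show the order of magnitude, not an estimate for this trial. PFS is a secondary endpoint, and the complete response analysis is not affected. The change should be made, but the trial's primary conclusion does not depend on it.

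**What to change.** - Reconcile Protocol Table 4 footnote 11, Sections 11.3 and 14, SAP 1.3 footnote 11, and the PFS text and table in SAP 3.3.7, including whether unrecorded assessments means all discontinuations or only those for an AE.
- Record the pathological stage from the existing cystectomy report at the 13-weekly contact. The cystectomy date is already needed for cystectomy-free days.
- Add a PFS row to the SAP: cystectomy specimen showing T2 or more advanced disease; date of cystectomy; event. State that it applies whether or not study drug had stopped.
- State how a cystectomy without progression is censored in PFS.
- If stage cannot be retrieved for some subjects, give their number and report the limitation with the PFS result.

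The cost is one data field, one SAP row and a slightly less favourable PFS. No new procedure is involved. One asymmetry would remain: upstaging after discontinuation would count while deaths after discontinuation would not. The SAP should explain this or remove it when the PFS text is reconciled.
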